11.3 Handling of missing/unobtainable data

All efforts will be made to collect a complete set of data by employing 2-4 week flexibility in scheduling and repeating inadequate quality MRI scans.

In the event that particular data points are missing for reasons other than inability to perform the test (i.e. because of disability) we will replace the missing data according to following algorithm:

- a. For data obtained every 6 months (i.e. clinical data and brain MRI data), the missing time point will be substituted by the average of 2 adjacent time-points: i.e. 6 months before and 6 months after the missing time-point. If the last time-point is missing (i.e. month 36), we will substitute the data for this time-point by the average of 2 preceding time-points.
- b. For data obtained once at treatment phase (i.e. CSF and apheresis data), the missing data cannot be replaced and the patient will be eliminated from analysis.

Handling data missing because the patient was unable to perform the test due to disability: this may happen for clinical tests such as timed 25 foot walk (25FW), 9 hole peg test (9HPT) and PASAT. These data will be calculated using the following recommendations from scoring instructions for the MSFC:

- a. 25FW: the inability to perform 25FW will be substituted by the largest Z-score in the MSFC Task force database (i.e. with the slowest time of any patient in the combined dataset used by the Task Force in its published meta-analysis). The largest Z-score in the

Task Force dataset is 13.7, therefore, for a subject who could not complete the 25FW Z_{leg} , average = -13.7 will be used.

- b. 9HPT: the inability to perform 9HPT will be coded as 777 and the following Z-score calculation formula will be applied:

$$Z_{arm, trial\#} = [(1/777 - \text{Baseline mean (1/9HPT)}) / \text{Baseline SD (1/9HPT)}]$$

- c. PASAT: In the event an individual patient cannot complete PASAT-3 due to disability, a score of 0 will be assigned.

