The measurement and collection of data will be performed as in the randomized trial. Quantitative neuroimaging measures of central nervous system (CNS: i.e. brain and spinal cord) tissue destruction and clinical and functional measures of neurological disability will be collected every 6-12 months. Additionally, biomarkers focusing on analysis of reactive oxygen species (ROS) and oxidative stress will be collected every 12 months. The primary outcome measure defined in the IPPoMS trial will be also utilized in IPPoMS-E. For patients originally randomized to placebo, patient-specific slopes of disease progression during 2 years of placebo therapy (as measured by primary and secondary outcomes) will be compared to patient-specific slopes of disease progression during 1 year of open label idebenone therapy. Combination of IPPoMS and IPPoMS-E trials will significantly expand paired “no therapy” vs. “idebenone therapy” CSF samples for biomarker studies. It will also provide (for the subgroup of subjects who were originally randomized to idebenone) longitudinal CSF samples on idebenone therapy (collected 2 years apart). This will allow calculations of intra-individual changes in CSF biomarkers on and off idebenone therapy, which may provide important insight into the mechanism of action of idebenone in PP-MS.

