7.4 Study design

Patients will be given idebenone (2250 mg/day, given as five 150 mg tablets, three times a day) and will be followed by combined neurological, neuroimaging and research biomarker/immunological evaluations every 6 months for 1 year. In addition, patients will have safety labs drawn at month 25 which can be drawn at NIH or at an outside lab with results (including normal values) communicated to NIH investigators. Telephone interviews will occur 1 week, 1 month (Mo 25) and 2 months (Mo 26) after initiation of dosing. Patient's safety and change in neurological function will be assessed during the telephone interview with an investigator (Figure 2).

The IPPoMS-E Baseline information will be provided by the results of the IPPoMS Month 24 assessments.

The time commitment will include extension of the last visit on IPPoMS trial (which will serve as initial visit in IPPoMS-E trial) and 2 additional prolonged outpatient or inpatient visits in the 1 year

period. Each prolonged visit will have procedures that together last at least 8 hours spread over 1-3 days.

According to negotiated MCRADA, Santhera Inc. will supply sufficient amount of idebenone for completion of the proposed trial (i.e. 1 year dosing for up to 85 patients). There is no negotiated provision for Santhera to continue to provide drug on a compassionate basis for any of the patients after completion of the trial.

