10. OUTCOME MEASURES

10.1 Primary outcome measure:

The IPPoMS trial has an adaptive design that will determine the primary outcome measure for the IPPoMS protocol based on pre-determined analysis of the quantitative clinical and neuroimaging secondary outcome measures in the first 30 subjects who finish 1 year of pre-treatment baseline. This analysis is expected to be concluded in the spring/summer of 2013. The primary outcome measure that comes out of the pre-determined analysis in the IPPoMS trial will be adopted as primary outcome measure in the IPPoMS-E trial.

10.2 Secondary outcome measures:

10.2.1 Neuroimaging outcomes:

1. Inhibition of individualized rates of development of brain atrophy: effect of idebenone on individualized rates of development of brain atrophy
2. Inhibition of individualized rates of development of brain gray matter atrophy: effect of idebenone on individualized rates of development of segmented gray matter atrophy
3. Inhibition of individualized rates of enlargement of ventricular volume: effect of idebenone on individualized rates of enlargement of segmented volume of 3rd ventricle
4. Inhibition of individualized rates of development of cervical SC atrophy: effect of idebenone on individualized rates of development of SC atrophy
5. Inhibition of individualized rates of neuroaxonal destruction as assessed by T1 relaxation time in the brain (ROI in normal appearing white matter and in deep gray matter): effect of idebenone on individualized rates of neuroaxonal destruction

6. Inhibition of individualized rates of neuroaxonal destruction as assessed by T1 relaxation time in the cervical spinal cord: effect of idebenone on individualized rates of neuroaxonal destruction
7. Inhibition of individualized changes in axonal integrity as assessed by axial diffusivity and of changes in myelin integrity as assessed by radial diffusivity on brain DTI imaging: effect of idebenone on individualized rates of neuroaxonal destruction

10.2.2 Clinical/functional outcomes:

1. Progression of lower extremity disability as assessed by 25 foot walk component of MSFC (comparing area under curve (AUC) between 1 year of pre-treatment baseline collected during IPPoMS trial and one year of idebenone therapy)

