11.2 Statistical analyses of outcome measures

Descriptive methods will be used to analyze the safety data. Generally, for the analysis of efficacy data in IPPoMS-E protocol, we will utilize equivalent outcomes collected during IPPoMS trial.

For primary and secondary outcome measures, we will use identical statistical approach as utilized in IPPoMS trial: i.e. in order to utilize all collected data, we will calculate areas under curve (AUC) values for each outcome, normalized per 1 year of “therapy”. Thus, we will calculate AUC for three different “treatments”: pre-treatment baseline (B), placebo (PI) and for idebenone (I) treatment. We will compare intra-individual changes in AUC values by following linear mixed effect model:

$AUC_{\text{outcome}} = \text{treatment (B, PL, I)} + \text{group} + \text{interaction between treatment and group} + \text{covariates}$

where “group” refers to original “placebo” versus “idebenone” groups from IPPoMS trial and the random part is patient. While randomization is stratified for age and therefore, we are expecting that the placebo and active treatment groups will be well-matched for age, we will use Age and sex as covariates in the model if we detect any interaction.

In addition to analysis of primary and secondary outcomes, combining data collected during IPPoMS and IPPoMS-E studies will significantly enhance our ability to detect treatment-related changes in CSF biomarkers. Depending on how many subjects choose to participate in IPPoMS-E, the amount of paired (i.e. no treatment versus idebenone) CSF samples may theoretically increase up to 2 fold in comparison to IPPoMS trial. Therefore, the cohort of patients originally assigned to placebo can be utilized as “confirmatory” cohort for biomarker changes identified in the IPPoMS trial. This would effectively increase the power for detecting significant differences, as only those biomarkers found to be significantly changed during the IPPoMS trial would be tested in the IPPoMS-E trial, thus limiting the number of multiple comparisons that would need to be performed (and for which p values need to be properly adjusted). Again, the differences in selected CSF biomarkers between “no-treatment”, “placebo” and “idebenone” treatment would be analyzed using the same mixed effect model.

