Finally, combining CSF data from IPPoMS with IPPoMS-E will provide two different longitudinal datasets: for patients originally randomized to placebo, we will have three CSF samples off therapy (Mo -1: baseline, Mo 12&24: placebo) and for patients originally randomized to idebenone, we will have three CSF samples (Mo12, 24 and 36). These longitudinal data will allow us to calculate “slope” of progression and compare these slopes between two different treatments using again linear mixed model:

$\text{Biomarker} = \text{time} + \text{treatment} + \text{interaction between time \& treatment} + \text{covariate}$

where “treatment” is either idebenone or no idebenone (i.e. pre-treatment baseline + placebo). The interaction between treatment and time will assess if the slopes for two treatments are parallel or not. It has been suggested that evaluating changes in the “slope” of progression may distinguish true ongoing neuroprotective effect from static “symptomatic” effect (*Machado, Murray et al. 1999; Ginsberg 2008*). In other words, under hypothetical scenario that idebenone may prove efficacious in PP-MS, its effect on disability may vary depending on the pathophysiology of the disease. There are two possible scenarios:

1. That idebenone enhances ATP production in neurons, soon after initiation of its dosing, and this enhances electrical conduction in demyelinated axons. The result would be improvement in neurological function. However, if enhancement of ATP production does not also lead to neuroprotection, then the “slope” of progression after initiation of idebenone therapy would be parallel to the “slope” of progression off therapy. In other words, the efficacy on the outcome would be “static” – resetting the baseline, but not changing the “slope” (Figure 3A).
2. That idebenone enhances ATP production in neurons, oligodendrocytes and astrocytes. This may, to some degree, protect all CNS cells from death. As death of neurons and oligodendrocytes continues on a progressive basis, a true neuroprotective drug will inhibit

the slope of the measured outcome (e.g. progression of disability or CNS tissue destruction) in comparison to no treatment. Such dynamic effect would lead to a greater absolute difference in the outcome with greater duration of therapy (Figure 3B). Finally, the drug may have both symptomatic and neuroprotective effects (Figure 3C).

[figure not shown]

Figure 3:

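### The interior imputation rule crosses the treatment switch: for an ex-placebo patient a missing Month 24 baseline is filled partly with an on-idebenone value

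*Combined protocol and SAP*

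**What the plan says.** Section 11.3(a) covers data collected every 6 months, namely clinical and brain MRI data. A missing visit is "substituted by the average of 2 adjacent time-points: i.e. 6 months before and 6 months after the missing time-point". The one exception begins "If the last time-point is missing (i.e. month 36"; that visit takes the mean of the two preceding ones. Nothing is said about a visit at which treatment changes.

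Section 7.4 gives Month 24 its role: "The IPPoMS-E Baseline information will be provided by the results of the IPPoMS Month 24 assessments". Follow-up is then "every 6 months for 1 year", so the on-drug visits are Months 30 and 36.

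The plan describes the efficacy contrast in three ways:

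- Section 3.4 compares "patient-specific slopes of disease progression during 2 years of placebo therapy" with slopes over 1 year of open-label idebenone, for primary and secondary outcomes in ex-placebo patients.
- Section 11.2 says "we will calculate areas under curve (AUC) values for each outcome, normalized per 1 year of" therapy, and models the AUC for baseline, placebo and idebenone periods.
- Section 10.2.2 defines each clinical secondary outcome by "comparing area under curve (AUC) between 1 year of pre-treatment baseline collected during IPPoMS trial and one year of idebenone therapy".

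Section 11.2 does not say whether the AUC is taken on the raw level or on change from the start of the period.

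**The concern.** Averaging the two neighbours is harmless when all three visits lie on one straight line. At Month 24 in an ex-placebo patient they need not: Month 18 is on placebo and Month 30 follows 6 months of idebenone. If the drug has any effect, the filled value carries some of it. Month 24 is both the last placebo value and the first value of the open-label year, so the error enters both sides of the comparison. At stake is the estimated effect in the affected patients, and whether its distortion has a known direction.

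**Working it through.** The documents state no figure on this point, so there is none to reproduce. The check is a noise-free calculation for one ex-placebo patient with linear progression at rate s per year.

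**Inputs.** Fill rule: section 11.3(a). On-drug visits at Months 30 and 36: section 7.4. Effect shapes: section 11.2, which describes a static effect as "resetting the baseline, but not changing the" slope, and a neuroprotective effect that changes the slope. Assumed, because the parent protocol is not supplied: visits at Months -12, -6 and 0 (baseline) and 0, 6, 12, 18 and 24 (placebo).

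**Error in the filled value.** Fill = (Y18 + Y30)/2.

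- No drug effect: the fill equals Y24, so there is no bias.
- Static step d: Y30 carries d, so the fill is off by d/2.
- Slope effect b per year: Y30 carries b/2, so the fill is off by b/4.

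**Slope contrast (section 3.4).** The placebo slope uses times 0, 0.5, 1, 1.5 and 2 years. The sum of squares about the mean is 1 + 0.25 + 0 + 0.25 + 1 = 2.5, so Month 24 has weight 1/2.5 = 0.4 per year. With three equally spaced visits the open-label slope is Y36 - Y24.

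- Slope effect: (b - 0.25b) - 0.4 × 0.25b = 0.65b. With complete data it is b, so 35% is lost.
- Step: (d - 0.5d) - 0.4 × 0.5d = 0.30d, where complete data would show 1.0d.

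**Raw-level AUC per year (section 11.2), trapezoid.** Open-label weights are 0.25, 0.5 and 0.25 on Months 24, 30 and 36. Month 24 has weight 0.25/2 = 0.125 in the 2-year placebo AUC and none in the pre-treatment baseline AUC.

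- Step, complete data: 0.5d + 0.25d = 0.75d. Filled: 0.75d + 0.25 × 0.5d = 0.875d. Minus placebo (0.125 × 0.5d = 0.0625d) this is 0.8125d.
- Slope effect, complete data: 0.5 × 0.5b + 0.25b = 0.5b. Filled: 0.5b + 0.25 × 0.25b = 0.5625b. Minus placebo (0.125 × 0.25b = 0.03125b) this is 0.53125b.

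**AUC of change from period start.** Subtract the filled error from the open-label AUC.

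- Step: 0.875d - 0.5d = 0.375d; minus placebo, 0.3125d.
- Slope effect: 0.5625b - 0.25b = 0.3125b; minus placebo, 0.28125b.

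| Contrast in the affected patient | Step: complete → filled | Slope effect: complete → filled |
|---|---|---|
| Slopes, idebenone vs 2-year placebo | 1.0d → 0.30d | 1.0b → 0.65b (-35%) |
| Raw AUC vs placebo | 0.75d → 0.8125d (+8.3%) | 0.5b → 0.531b (+6.3%) |
| Raw AUC vs 1-year baseline | 0.75d → 0.875d (+16.7%) | 0.5b → 0.5625b (+12.5%) |
| Change AUC vs placebo | 0.75d → 0.3125d (-58%) | 0.5b → 0.281b (-44%) |
| Change AUC vs 1-year baseline | 0.75d → 0.375d (-50%) | 0.5b → 0.3125b (-37.5%) |

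**Two repairs that do not work.**

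- Filling Month 24 with the mean of Months 12 and 18 gives the value at Month 15, which is 0.75 year behind. With an inert drug the open-label slope gains 0.75s and the placebo slope loses 0.4 × 0.75s = 0.3s, so the slope contrast is biased by 1.05s.
- Computing the open-label AUC from Months 30 to 36 alone centres it on Month 33 instead of Month 30. That shifts the raw level by 0.25s with an inert drug.

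**The case against.** A reader might infer that the rule removes 35-70% of the treatment effect, or that the trial's effect is understated. The documents do not support either as a general statement. The loss belongs to the section 3.4 slope comparison; under section 11.2 on raw-level AUC the same fill slightly enlarges the contrast. The 70% end is also weak on its own terms. Section 11.2 defines a static effect as one that leaves the slopes parallel, so a step appears in the slope contrast only because a pre-drug visit anchors the open-label slope. Within section 11.2 slopes are used only for CSF biomarkers, and 11.3(b) does not impute those.

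The trigger should also be rare. Month 24 is the consent and entry visit, section 6.2 requires completion of the parent study, section 7.5.1 allows a 4-week window either side, and section 11.3 provides for repeating inadequate scans and handles disability-related gaps separately. Month 24 is also the parent trial's last visit, and its missing-data rule is not supplied. The same gap means that nothing firm can be said about a missing Month 0 in the original idebenone arm. Finally, section 7.6.1 stops the extension for futility.

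These points limit the size and the direction, and they stand. They do not remove the defect: read as written, the rule treats Month 24 as interior and uses an on-drug value for a pre-drug baseline. Single tests or scans can still be missing at an attended visit. If the parent trial fills Month 24 differently, the same visit has two imputed values. Section 7.6.1 also transfers the data for continued analysis, so the rule may still be applied.

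**Conclusion.** The point holds as a minor one. Section 11.3(a) gives a wrong value at Month 24 for an ex-placebo patient whenever the drug has an effect. In such a patient, with both neighbouring visits observed, the slope contrast falls to 0.65 of a true slope effect, and a static step shows as 0.3 instead of 1.0 of the step. The AUC contrast is either enlarged (about 6-8% against placebo, 12.5-17% against the 1-year baseline) or reduced (about 44-58% and 38-50%), depending on an AUC definition the plan leaves open. These figures rest on linear progression, a 6-monthly placebo visit grid and the two effect shapes named in section 11.2. With an inert drug and linear progression there is no bias, so the rule does not create a false positive. The documents give no rate of missing Month 24 values, so no average effect on the trial result can be stated.

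**What to change.** Add one sentence to section 11.3(a): *No value is imputed across a change of treatment.*

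Leave a missing Month 24 unfilled in ex-placebo patients. Estimate that patient's contribution from a visit-level linear mixed model on the observed visits, with time, treatment, their interaction and random patient effects. Section 11.2 already sets out a linear mixed model with these fixed terms for CSF biomarkers. State whether the AUC is on the raw level or on change from period start. Do not substitute the mean of Months 12 and 18, and do not compute the open-label AUC from Months 30 to 36 alone.

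The cost is a little more than the one sentence. The few affected patients contribute fewer values, and a visit-level model has to be specified alongside the per-period AUC model.

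### Filling a missing month 36 with the mean of months 24 and 30 understates worsening in the extension year, and the CSF elimination rule is not limited to the paired comparison

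*Combined protocol and SAP*

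**What the plan says.** Section 11.3 gives two rules for data missing for reasons other than inability to do the test. Rule (a) covers clinical and brain MRI data collected every six months. An interior gap takes the mean of its two neighbours. At the end of follow-up the rule is: "If the last time-point is missing (i.e. month 36), we will substitute the data for this time-point by the average of 2 preceding time-points". On this schedule those are months 24 and 30. Tests missed through disability have their own scoring rules and are outside this point.

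Rule (b) has the scope "For data obtained once at treatment phase (i.e. CSF and apheresis data" and the consequence "the missing data cannot be replaced and the patient will be eliminated from analysis".

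These rules feed the following analyses:

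- Section 11.2, primary and secondary outcomes: "we will calculate areas under curve (AUC) values for each outcome, normalized per 1 year of" treatment, for baseline, placebo and idebenone periods, compared in a linear mixed model with group and the treatment-by-group interaction. Section 10.2.2 describes the clinical outcomes as "comparing area under curve (AUC) between 1 year of pre-treatment baseline collected during IPPoMS trial and one year of idebenone therapy".
- Section 3.4, original-placebo patients: slopes over two placebo years against slopes over one idebenone year. Section 5.2 sets a three-year off-drug period against the idebenone year.
- Section 11.2, CSF slopes in a linear mixed model: "for patients originally randomized to placebo, we will have three CSF samples off therapy", and "for patients originally randomized to idebenone, we will have three CSF samples (Mo12, 24 and 36".

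Section 7.4 takes the parent trial's month 24 as the extension baseline. Section 7.6.1 records the futility stop and a final visit with a clinical examination and MRI. Neither that section nor the flow chart in Appendix A lists a lumbar puncture at that visit.

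**The concern.** In a disease expected to worsen, the mean of two earlier visits is a poor stand-in for a later one: it pulls the last value back in time. The interior rule has no such fault on a straight line, so the distortion is confined to the extension year, which is the idebenone year in the period comparisons. For original-placebo patients, half of the filled value is a measurement taken before any idebenone. A drug with no effect could then appear to slow worsening, and the constructed value enters the model as if it had been observed, so the standard error does not reflect the missing visit.

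The CSF rule raises a different problem. It treats CSF as collected once on treatment, but section 11.2 lists three on-drug samples for the original-idebenone group. Removing a patient for one missing sample discards data that the slope model could use.

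**Working it through.** **Inputs.** The fill rule is from 11.3, the month-24 baseline from 7.4, and the AUC per year from 11.2. Neither the rate of worsening b (per year) nor the share f with month 36 missing is given. Assumptions: parent-trial visits every six months from month -12; a steady course with value b × years from month 0; higher is worse (mirror the sign for volumes or scores that fall); no drug effect unless stated.

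**The filled value.** True months 24, 30 and 36 are 2b, 2.5b and 3b. The fill is (2b + 2.5b)/2 = 2.25b, which is the month-27 value. The error is 2.25b − 3b = −0.75b. A missing month 30 would be filled with (2b + 3b)/2 = 2.5b, which is exact.

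**Idebenone-year AUC (trapezoid).** True: 0.25(2b) + 0.5(2.5b) + 0.25(3b) = 2.5b. Filled: 0.25(2b) + 0.5(2.5b) + 0.25(2.25b) = 2.3125b. The shortfall is 0.1875b, or 2.25 months of progression. Mean levels for comparison: baseline year −0.5b, placebo years 1.0b, three-year off-drug period 0.5b.

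| Quantity, per affected patient | True | Filled | Understated by |
|---|---|---|---|
| Raw AUC, idebenone minus baseline year | 3.0b | 2.8125b | 6.25% |
| Raw AUC, idebenone minus three-year off-drug period | 2.0b | 1.8125b | 9.4% |
| Raw AUC, idebenone minus placebo | 1.5b | 1.3125b | 12.5% |
| Original idebenone, raw AUC over three years minus baseline year | 2.0b | 1.9375b | 3.1% |
| AUC of change from month 24 | 0.5b | 0.3125b | 37.5% |
| Slope, months 24 to 36 | b | 0.25b | 75% |

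**Group level.** Multiply by f. At an assumed f of 5–30%: 0.3–1.9% against the baseline year, 0.6–3.8% against placebo, 1.9–11.3% for AUC of change, 3.8–22.5% for the slope.

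**Direction.** Section 11.2 allows for an effect "resetting the baseline, but not changing the" slope. Suppose an original-placebo patient gains s years of progression at once on idebenone. The fill is then (2b + 2.5b − sb)/2 and the true value 3b − sb. The error is −0.75b + 0.5sb, which is zero at s = 1.5 and works against idebenone beyond that. For a stable patient b = 0 and the error is nil.

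**CSF rule.** The time-by-treatment variance was compared with and without deletion, by generalised least squares with a random intercept and an assumed within-patient correlation of 0.3–0.8. With the three samples per arm listed in 11.2, deleting original-idebenone patients who lack month 36 inflates the variance by a factor of 1.016–1.022 at 10% missing and 1.067–1.086 at 30%. If all four samples per patient were modelled, the factors would be 1.08 and 1.28–1.29.

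**The case against.** The strongest reply is about size. Section 11.2 specifies AUC and mentions no baseline correction, so the small raw-AUC percentages are the ones that apply. The 75% figure belongs only to the slope comparison in the precis (3.4), since section 11.2 plans slope models for CSF alone. The 37.5% figure needs an AUC of change that the plan does not state. Missingness may also be low. The only attrition figure is 85 enrolled to yield 66 completers (11.5), a loss of 19/85 = 22.4%. Spread over a baseline year and two dosing years, that is about 8% a year or 4% per six months. At 4–8% missing, the raw-AUC error is 0.25–0.5% against baseline and 0.5–1.0% against placebo. All of this stands.

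Three stronger readings are tempting and are not supported:

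- That month 36 is on drug for everyone. Section 9.3 (items 3 and 4) stops treatment in some patients and follows them off therapy for outcomes.
- That a measured final visit under 7.6.1 is overwritten by a fill. Section 11.3 does not mention that visit, and nothing says that its data are discarded. The gap is one of silence, and the number of patients affected is not given.
- That rule (b) removes patients from the CSF slope model. The text does not say so; it simply sets no limit. Elimination is right for apheresis and for the paired comparison, where an original-placebo patient without month 36 has no pair. Month 36 is not among the samples 11.2 lists for that group's slope.

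It can also be said that 11.2 deliberately carries over the parent trial's method. That is a reason to keep the model's structure, but it does not justify a last-visit rule that is biased for a progressive outcome.

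**Conclusion.** The last-visit substitution is wrong as written for a worsening outcome. Under steady progression it gives the month-27 value and understates the idebenone-year AUC by 0.1875b per affected patient, which is 6.25% of the difference from baseline and 12.5% of the difference from placebo before multiplying by the unknown missing fraction. The direction depends on the course: it favours idebenone while patients are worsening, not in every patient. The larger percentages hold only for an AUC of change or for the precis slope comparison. A reader might infer that the rule could by itself produce a convincing drug effect; on the AUC analysis as specified, the documents do not support that.

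Rule (b) needs a stated limit. With the samples listed in 11.2 its cost is about 2% of variance at 10% missing and 7–9% at 30%.

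The point should be fixed but is modest. The trial stopped for futility, although 7.6.1 moves its data and samples to another protocol for further analysis.

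**What to change.** 1. In 11.3(a), delete the last-visit substitution. Fit a likelihood-based linear mixed model with a random patient effect to the observed visits, keeping the baseline, placebo and idebenone levels of 11.2, group, their interaction and the covariates. Visit-by-group means would do this. If time is modelled linearly, include a post-month-0 term in both arms besides the idebenone terms. Without that term, an assumed 0.5b placebo response and no drug effect gives a spurious idebenone step of −0.13b to −0.15b and a spurious time-on-idebenone term of +0.085b to +0.18b. In that same model, filled data give a spurious time-on-idebenone term of −0.010b to −0.062b at 5–30% missing.

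2. Report AUC as contrasts of the model's estimated means, with weights 0.25, 0.5 and 0.25 at months 24, 30 and 36 for the idebenone year and the model-based standard error. State whether AUC is baseline-corrected. Enter a measured 7.6.1 final visit at its actual date, and state how patients followed off therapy under 9.3 are coded.

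3. In 11.3(b), limit elimination to the paired on/off CSF comparison and apheresis, and keep all available CSF samples in the slope model of 11.2.

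4. Add one sensitivity analysis that assumes data not missing at random, since the likelihood approach relies on missing at random.

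No new visit or sample is needed. The costs are analysis work, slightly larger standard errors (a real loss of information that the fill hides), and a departure from the parent trial's statistical method.
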